2.1.7 Pharmacodynamic/genomics endpoints

Serum total IgE, antigen-specific IgE, antigen-specific IgG4 panel, and Thymus and Activation-Regulated Chemokine (TARC) will all be assayed at Visit 2(Week 0), (TARC only Visit 8 (Week 12)), Visit 14 (Week 28), and EOT (Week 52).

Fractional exhaled nitric oxide (FeNO) will be analyzed using a NIOX instrument (Aerocrine AB, Solna, Sweden), or similar analyzer using a flow rate of 50 mL/s, and reported in parts per billion (ppb). This assessment should be conducted prior to spirometry and following a fast of at least 1 hour at Visit 1(Week -4±1), Visit 2 (Week 0), Visit 3 (Week 2), Visit 4 (Week 4), Visit 5 (Week 6), Visit 6 (Week 8), Visit 7 (Week 10), Visit 8 (Week 12), Visit 10 (Week 16), Visit 12 (Week 20), Visit 14 (Week 24), Visit 16 (Week 28), Visit 18 (Week 32), Visit 20 (Week 36), Visit 22 (Week 40), Visit 24 (Week 44), Visit 26 (Week 48), Visit 28 (Week 52), Visit 29 (Week 56), Visit 30(Week 60), Visit 31(Week 64).

Blood eosinophil counts from hematology assays will be collected at Visit 1(Week -4±1), Visit 2 (Week 0), Visit 8 (Week 12), Visit 14 (Week 24), Visit 20 (Week 36), Visit 28 (Week 52), Visit 31(Week 64) and early termination.

[REDACTED]

2.1.8 Humoral immune response to vaccines

Humoral immune responses to standard vaccines (in this study: any vaccination for tetanus, diphtheria, pertussis and/or seasonal trivalent/quadrivalent influenza vaccine) occurring during dupilumab treatment will be evaluated for those patients eligible for these vaccinations.

Any patient who will receive planned vaccination for tetanus, diphtheria, pertussis and/or seasonal trivalent/quadrivalent influenza during the study, will be scheduled to receive the respective vaccination(s) and to have blood samples for antibody titers drawn before and after the respective vaccination(s), as detailed below.

Scheduled blood sample collection for pre- and post-vaccine antibody titers, for both vaccinations (ie, any tetanus, diphtheria and pertussis and/or seasonal trivalent/quadrivalent influenza) should be drawn within 8 weeks prior to vaccination and at 3-4 weeks (up to 6 weeks) after the respective vaccination(s); however, all blood titer samples must be drawn between Week 6 and Week 50 (ie, Visit 5 and Visit 27, respectively).

2.1.9 Health economic endpoints

The Health Care Resource Utilization (HCRU) questionnaire (questions on use of reliever medication, specialist visit, hospitalization, emergency or urgent medical care facility visit, outcome, school days' loss, etc), as integrated part of the e-CRF, will be administered at Visit 2, Visit 8, Visit 14, Visit 20, Visit 26, Visit 28 and Visit 31, and will additionally be used to assess HCRU in the event of any asthma exacerbation: severe asthma exacerbation event or evidence of LOAC (for detailed definitions see [Section 2.1.3.1](#)).

2.2 DISPOSITION OF PATIENTS

This section describes patient disposition for patient study status.

Screened patients are defined as any patients that have signed the informed consent.

Randomized patients consist of all patients with a signed informed consent form who have had a treatment kit number allocated and recorded in the IRT database, regardless of whether the treatment kit was used.

For patient study status, the total number of patients in each of the following categories will be presented in the clinical study report summary table:

- Screened patients
- Screen failure patients and reasons for screen failure
- Nonrandomized but treated patients
- Randomized patients
- Randomized but not treated patients
- Randomized and treated patients
- Patients who did not complete the 52-week treatment as per protocol
- Patients who discontinued study treatment by main reason for permanent treatment discontinuation
- Patients who withdraw from study prior to Week 52
- Patients who withdraw from study prior to Week 52 by main reason for study discontinuation.
- Patients who withdraw from study
- Patients who rolled over to the LTS14424 study
- Patients who withdraw from study by main reason for study discontinuation
- Death at last study contact

For all categories of patients (except for the screened and nonrandomized categories) percentages will be calculated using the number of randomized patients as the denominator. Reasons for treatment discontinuation, including due to the COVID-19 pandemic, will be supplied in tables giving numbers and percentages by treatment group. This summary will be provided by treatment group and may also be further subgrouped by region/stratum as applicable.

All critical or major deviations will be summarized in tables giving numbers and percentages of deviations by deviation category for each treatment group. Critical or major deviations that are related to the COVID-19 pandemic will be summarized in a similar manner.

2.2.1 Randomization and drug dispensing irregularities

Randomization and drug-dispensing irregularities occur whenever:

1. A randomization is not in accordance with the protocol-defined randomization method, such as a) an ineligible patient is randomized, b) a patient is randomized based on an incorrect stratum, c) a patient is randomized twice, or d) in a dynamic randomization scheme the treatment assignment is, in fact, not random, due to a computer program error.

OR

2. A patient is dispensed an IMP kit not allocated by the protocol-defined randomization, such as a) a patient at any time in the study is dispensed a different treatment kit than as randomized (which may or may not contain the correct-as-randomized IMP), or b) a nonrandomized patient is treated with IMP reserved for randomized patients.

Randomization and drug-dispensing irregularities will be monitored throughout the study and reviewed on an ongoing basis.

All randomization and drug-dispensing irregularities will be documented in the clinical study report. If the number of irregularities is large enough to make a tabular summary useful, the irregularities will be categorized and summarized among randomized patients (number and percentages). Nonrandomized, treated patients will be described separately.

Randomization and drug-dispensing irregularities to be prospectively identified include but are not limited to:

Randomization and drug allocation irregularities
Kit dispensation without IRT transaction
Erroneous kit dispensation
Kit not available
Randomization by error
Patient randomized twice
Stratification error
Patient switched to another site

2.3 ANALYSIS POPULATIONS

Patients treated without being randomized will not be considered randomized and will not be included in any efficacy population, but will be included in the safety population.

The randomized population includes any patient who has been allocated to a randomized treatment regardless of whether the treatment kit was used.

For any patient randomized more than once, only the data associated with the first randomization will be used in any analysis population. The safety experience associated with any later randomization will be assessed separately.

2.3.1 Efficacy populations

The full intent-to-treat (ITT) population is defined as all randomized patients.

Type 2 inflammatory asthma phenotype population is defined as the randomized patients with baseline blood eosinophils ≥ 0.15 Giga/L or baseline FeNO ≥ 20 ppb.

Baseline blood eosinophils ≥ 0.3 Giga/L population is defined as the randomized patients with baseline blood eosinophils ≥ 0.3 Giga/L.

Baseline blood eosinophils ≥ 0.15 Giga/L population is defined as the randomized patients with baseline blood eosinophils ≥ 0.15 Giga/L.

Baseline FeNO ≥ 20 ppb population is defined as the randomized patients with baseline FeNO ≥ 20 ppb.

All efficacy endpoints will be analyzed based on both the population with a Type 2 inflammatory asthma phenotype and the population with baseline blood eosinophils ≥ 0.3 Giga/L. For selected efficacy endpoints, the analysis will be done for all four efficacy populations. For detailed analysis plan, refer to [Appendix M](#). For the analysis of primary efficacy endpoint, the testing hierarchy will start with the patients with baseline blood eosinophils ≥ 0.3 Giga/L population for the US and US reference countries; For EU and EU reference countries, the testing hierarchy will start with the Type 2 inflammatory asthma phenotype population (patients with baseline blood eosinophils ≥ 0.15 Giga/L or baseline FeNO ≥ 20 ppb). For more details about multiplicity consideration, refer to [Section 2.4.4.4](#).

Patients will be analyzed in the treatment group to which they are randomized.

For PRO endpoints which are only valid on specific subpopulations of patients, only patients within the subpopulation will be analyzed according to their randomized treatment group. Such subpopulations include patients of age ≥ 7 years old at randomization for PACQLQ(S) and patients with history of allergic rhinitis for PRQLQ-IA.

If a patient is unblinded during the study, only data obtained before the unblinding will be included in the efficacy analyses.

2.3.2 Safety population

The safety population is defined as:

- All patients who actually received at least 1 dose or part of a dose of the IMP, analyzed according to the treatment patients actually received.

In addition:

- Randomized patients for whom it is unclear whether they took the IMP will be included in the safety population as randomized.
- For patients on placebo but accidentally exposed to dupilumab, the treatment group allocation for as-treated analysis will be dupilumab group.
- If a patient is unblinded during the study, all safety data from the patient regardless of before or after unblinding will be included in the safety analyses according to the treatment patients actually received before the unblinding.

All analyses will be provided by treatment regimens as Dupilumab vs placebo. No planned analysis based on the subcategory of dose level will be provided.

2.3.3 Population for pharmacokinetics, immunogenicity, and pharmacodynamics analyses

The PK population will consist of all patients in the safety population with at least one non-missing serum concentration data. Patients will be analyzed according to the treatment actually received.

The ADA population will consist of all patients in the safety population who had at least one non-missing ADA results (either 'ADA negative' or 'ADA positive') after first dose of the study treatment. Patients will be analyzed according to the treatment actually received.

Biomarkers will be analyzed in the exposed population, consisting of patients in the safety population.

2.4 STATISTICAL METHODS

2.4.1 Demographics and baseline characteristics

The demographics, baseline characteristics and medical history will be presented for the population with Type 2 inflammatory asthma phenotype, population with baseline blood eosinophils ≥ 0.3 Giga/L, population with baseline blood eosinophils ≥ 0.15 Giga/L, population with baseline FeNO ≥ 20 ppb and full ITT population.

Continuous data will be summarized using the number of available data, mean, standard deviation (SD), median, minimum and maximum for each treatment group. Categorical and ordinal data will be summarized using the number and percentage of patients in each treatment group.

Parameters will be summarized on the randomized population analyzed in the treatment group to which they were randomized. Analyses for the safety population will be included in the appendices if the size of the safety population is different ($>10\%$) from the size of full ITT population in the primary analysis for any treatment group.

Parameters described in [Section 2.1.1](#) will be summarized by treatment group and overall treatment groups using descriptive statistics.

Medical and surgical history will be summarized by treatment group and by system organ class (SOC) and preferred term (PT) sorted by internationally agreed order of SOC and by the decreasing frequency of PT within SOC based on the overall incidence across treatment groups. Atopic medical history will be summarized separately.

No statistical testing on demographic and baseline characteristic data will be performed. P-values will not be calculated.

No specific description of either efficacy or safety parameters will be provided at baseline. If relevant, the baseline values will be described along with each efficacy or safety analysis.

2.4.2 Prior or concomitant medications

The general prior and concomitant medications, and controller medications will be presented for the population with Type 2 inflammatory asthma phenotype, and population with baseline blood eosinophils ≥ 0.3 Giga/L, and full ITT population.

Medications will be summarized by treatment group according to the WHO-DD dictionary, considering the first digit of the anatomic category (ATC) class (anatomic category) and the first 3 digits of the ATC class (therapeutic category). All ATC codes corresponding to a medication will be summarized, and patients will be counted once in each ATC category (anatomic or therapeutic) linked to the medication. Therefore patients may be counted several times for the same medication.

The table for prior medications will be sorted by decreasing frequency of ATC followed by all other therapeutic classes based on the overall incidence across treatment groups. In case of equal frequency regarding ATCs (anatomic or therapeutic categories), alphabetical order will be used.

Concomitant medication received during first IMP to last IMP +14 days and concomitant medication received during first IMP to last IMP +98 days will be summarized separately. The tables for concomitant medications will be sorted by decreasing frequency of ATC followed by all other therapeutic classes based on the incidence in the dupilumab group. In case of equal frequency regarding ATCs (anatomic or therapeutic categories), alphabetical order will be used.

In addition, inhaled corticosteroid in combination with other controllers and reliever medications will be summarized separately. Number of patients who have their controller medications permanently stepped-up during the study according to protocol will also be summarized and the time to first permanent step-up will also be summarized with descriptive statistics.

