9.4.2.1 Serum Biomarkers

Total IgE will be measured with a quantitative method (eg, ImmunoCAP) approved for diagnostic testing.

Antigen-specific IgE and antigen-specific IgG4 will be detected using panels of antigens appropriate to the location of the clinical site (quantitative ImmunoCAP test; Phadia).

TARC will be assayed with a validated immunoassay.

9.4.2.3 Patients Requiring a Permanent Step Up in Background Controller Medication After 2 or More Severe Asthma Exacerbation Events.

For this study, severe asthma exacerbation events should be managed by the Investigators based on their medical judgment and applicable national/international asthma management guidelines, and as outlined in this protocol:

For patient(s), who experience 2 or more severe asthma exacerbation events anytime during the Treatment Period, a permanent change (step up in medium-to high-dose ICS or addition of second controller for patients on high-dose ICS monotherapy) see [Appendix A](#) and [Appendix B](#)) on their stable-dose background controller medication may occur, as indicated and according to the respective Investigator's medical judgment and direction.

The proportion of all patients with any of these treatment adjustments will be compared by treatment arm.

9.4.2.4 Other Patient Reported Outcomes Including Health Related Quality of Life (Exploratory Endpoints)

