11.4.2.2.4 Analysis of Change from Baseline for Other Categorical Variables

Percentage of patients requiring increase in dose or addition of background medication will be analyzed as a categorical variable. Descriptive statistics by treatment group will be provided including the number and the percentage of patients in each category. Time to the first time requiring increase in dose or addition of background medication may also be provided by the Kaplan-Meier method if there are a sufficient number of patients requiring increase in dose or addition of background medication.

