1.2.3 Exploratory objectives

- To explore baseline and on-treatment levels of biomarkers for their potential to predict and to associate with a treatment response
- [REDACTED]
- To evaluate the proportion of patients requiring increased dose of inhaled corticosteroids (ICS) or step up in the second controller medication regimen
- To evaluate the effect of dupilumab on additional PROs

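### SAP 2.4.2 gives time to first permanent controller step-up as descriptive statistics with no censoring rule and does not carry forward the protocol's conditional Kaplan-Meier analysis, so the times cannot be compared between arms

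*SAP*

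**What the plan says.** SAP 2.4.2 is a medication-summary section covering the Type 2 phenotype population, the baseline eosinophils ≥0.3 Giga/L population and full ITT. On step-up it plans two things. The first is a count: "Number of patients who have their controller medications permanently stepped-up during the study according to protocol will also be summarized". The second concerns timing: "the time to first permanent step-up will also be summarized with descriptive statistics". It does not say which children contribute a time, or what is done with a child who never steps up or who leaves the study.

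The SAP's Cox and Kaplan-Meier section (2.4.4.3.2) refers to the events defined in SAP 2.1.3.2, which are first severe exacerbation and first loss of asthma control. SAP 2.4.4.5.2 adds first systemic corticosteroid use. Step-up is in neither.

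The protocol treats step-up in three places:

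- Protocol 9.4.1 makes the proportion stepped up an exploratory endpoint. SAP 1.2.3 has the matching objective: "To evaluate the proportion of patients requiring increased dose of inhaled corticosteroids (ICS) or step up in the second controller medication regimen".
- Protocol 9.4.2.3 says "The proportion of all patients with any of these treatment adjustments will be compared by treatment arm".
- Protocol 11.4.2.2.4 says "Percentage of patients requiring increase in dose or addition of background medication will be analyzed as a categorical variable" and then adds "Time to the first time requiring increase in dose or addition of background medication may also be provided by the Kaplan-Meier method", but only "if there are a sufficient number of patients requiring increase in dose or addition of background medication". No number is given for sufficient.

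Table 3 in SAP 1.6, which lists changes from the protocol's planned analyses, contains only the change to the FEV1 covariates.

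**The concern.** A step-up time exists only for a child who steps up, and the documents allow a step-up only after two or more severe exacerbations. A mean or median of those times therefore conditions on an event after randomization that treatment is meant to prevent. It compares two differently selected groups, and it has no place for children who were followed for a year without stepping up or who withdrew first. If non-steppers were instead included at their last day of follow-up, censored times would be averaged as though they were event times, which is no better.

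The count and percentage have a smaller weakness: a child who withdraws is counted as not stepped up. If withdrawal differs between arms, the crude proportions are distorted.

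What is at stake is the reading of one descriptive table. A reader who sees near-equal average times in the two arms could conclude that dupilumab does not affect step-up when it does.

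**Working it through.** The documents state no rate, event count or power for step-up, so there is no figure to reproduce. The calculations below are illustrations. I treat the protocol's increase or addition of background medication and the SAP's permanent step-up as the same event.

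**Inputs from the documents.** 402 children, 268 dupilumab and 134 placebo; 20% linear discontinuation at 1 year, hence 0.9 year mean exposure (Protocol 11.1; SAP 1.3).

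**Assumed.** Exponential step-up times, hazard ratio 0.5, and placebo step-up by Week 52 of 5% to 30%.

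**Step 1: what the time summary would show.** With weekly placebo hazard λ = −ln(1 − p)/52, the mean time among those who step up by Week 52 is 1/λ − 52·e^(−52λ)/(1 − e^(−52λ)). For dupilumab, replace λ by λ/2. For p = 10%, λ = 0.002026, which gives 25.5 weeks on placebo and 25.8 on dupilumab. Expected events are 0.9 × (134·p + 268·p₁), where p₁ = 1 − e^(−26λ) is the dupilumab proportion. Log-rank power is Φ(√(events × 2/9) × ln 2 − 1.96).

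| Placebo stepped up | Dupilumab stepped up | Mean weeks, placebo vs dupilumab | Expected events of 402 | Log-rank power |
|---|---|---|---|---|
| 5% | 2.5% | 25.8 vs 25.9 | 12 | 0.21 |
| 10% | 5.1% | 25.5 vs 25.8 | 24 | 0.37 |
| 20% | 10.6% | 25.0 vs 25.5 | 50 | 0.63 |
| 30% | 16.3% | 24.5 vs 25.2 | 76 | 0.81 |

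The average times differ by less than a week in every row, while the proportions differ by nearly a factor of two.

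**Step 2: the same check with step-up placed at the second exacerbation.** This is a gamma-Poisson simulation with dispersion 1.5, rate ratio 0.5 and the 20% dropout. A placebo rate of 0.5 per year gives mean times of 29.4 vs 31.5 weeks and proportions of 10.2% vs 3.9%. A rate of 1.0 per year gives 26.5 vs 29.4 weeks and 21.4% vs 10.1%. The times now differ by 2 to 3 weeks; the proportions still differ at least twofold.

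**Step 3: how many children could contribute a time.** The current rate assumptions are redacted, so I use the superseded design (placebo rate 1.0, rate ratio 0.5, dispersion k = 1.5, 0.9 year) and vary the rate. For mean m, P(≥2) = 1 − (1 + km)^(−1/k) × [1 + m/(1 + km)].

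- Placebo, m = 0.90: 1 − 0.566 − 0.217 = 0.218; 134 × 0.218 ≈ 29.
- Dupilumab, m = 0.45: 1 − 0.709 − 0.190 = 0.101; 268 × 0.101 ≈ 27.
- Together about 56 of 402, or 14%.

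Placebo rates from 0.5 to 2.0 give about 24 to 109 children, or 6% to 27%. Because step-up after two exacerbations is discretionary, the number who actually step up should be smaller in each case.

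**Step 4: follow-up in the crude proportion.** Scaling by the 0.9 mean exposure, a true 10% by Week 52 appears as about 0.9 × 10% = 9%. If dropout is alike in both arms, the ratio between them is roughly kept. Distortion needs unequal dropout.

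**The case against.** The strongest reply is that this is a medication-use summary and not an efficacy analysis. The declared endpoint is the proportion over all patients, compared by arm, and the SAP reports the number stepped up in the same sentence as the time. That stands. A reader might infer that the trial cannot show a treatment difference in step-up. The documents do not support that, because the planned proportion would show it, as Steps 1 and 2 confirm.

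Second, a reader might infer that the SAP withdrew Kaplan-Meier. That is not shown either. Protocol 11.4.2.2.4 keeps it as an option, and SAP Table 3 does not list its removal. SAP 2.4.4.3.2 also says that untabulated secondary endpoints follow the strategy for their endpoint type. Protocol 11.4.2 lists the step-up percentage beside the secondary endpoints, though Protocol 9.4.1 calls it exploratory. What can be said is that the SAP text omits the option and leaves its condition undefined.

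Third, the SAP does not state that only children who stepped up are used. This is correct. It is the natural reading, and the alternative is no better, but it remains a reading.

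Fourth, it is tempting to say that the treatment-adherence analysis of exacerbations suffers, because follow-up there ends at step-up. It does not: that model takes each child's own duration as the offset (SAP 2.4.4.1) and never uses the 2.4.2 summary. Nor are the children without a step-up discarded from the trial's evidence. They stay in the denominator of the planned percentage.

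Finally, events will be few. At the superseded rates, only about 5 placebo and 3 dupilumab children would have had two exacerbations by Week 12. That limits early time points, and it is why the protocol made the analysis conditional.

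**Conclusion.** The point holds in limited form. The only method the SAP names for time to first permanent step-up cannot be interpreted as a comparison between arms, no censoring rule is given, and the protocol's conditional Kaplan-Meier analysis is not carried forward. In the illustrations a halved hazard or exacerbation rate moves the average time by less than 1 week (exponential times) or by 2 to 3 weeks (step-up at the second exacerbation). These sizes rest on assumed step-up proportions, superseded or assumed exacerbation rates, and the natural reading of who contributes.

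The consequence is small. The endpoint is exploratory, the planned proportion would reveal a difference, and step-up is not in either testing hierarchy (SAP Tables 9 and 10). The primary analysis, the key secondary analysis and the type I error are untouched.

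**What to change.** In SAP 2.4.2, replace the descriptive summary of time to first permanent step-up with the Kaplan-Meier cumulative proportion stepped up by arm, for example at Weeks 24, 36 and 52, with pointwise confidence intervals. Count from randomization. Censor children without a step-up at Week 52 or last contact, whichever is earlier, as SAP 2.1.3.2 does for first exacerbation. Use the three populations that 2.4.2 already lists, with all children in each at risk from randomization, to match the all-patients proportion in Protocol 9.4.2.3. Keep the count and percentage. No Cox model is needed.

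If the sponsor prefers to keep the protocol's condition, the SAP should state the minimum number of step-ups. If Kaplan-Meier is to be dropped, that belongs in SAP Table 3.

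The cost is one further run of a program already planned for other endpoints. The drawback is imprecision: with roughly 12 to 76 events in 402 children under the assumptions above, and fewer in the subpopulations, the intervals will be wide, above all early on.
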